## **10.0 Source Documents and Case Report Form Completion**

### **10.1 Source Documents**

Source documents are defined as original documents, data and records. This may include hospital records, clinical and office charts, laboratory data/information, subjects' diaries or evaluation checklists, pharmacy dispensing and other records, recorded data from automated instruments, microfiches, photographic negatives, microfilm or magnetic media, and/or x-rays. Data collected during this study must be recorded on the appropriate source documents.

The investigator(s)/institution(s) will permit study-related monitoring, audits, IEC/IRB review, and regulatory inspection(s), providing direct access to source data documents.

## **10.2 Case Report Forms**

Case report forms (CRF) must be completed for each subject screened/enrolled in this study. These forms will be used to transmit information collected during the study to AbbVie and regulatory authorities, as applicable. The CRF data for this study are being collected with an electronic data capture (EDC) system called Rave® provided by the technology vendor Medidata Solutions Incorporated, NY, USA. The EDC system and the study-specific electronic case report forms (eCRFs) will comply with Title 21 CFR Part 11. The documentation related to the validation of the EDC system is available through the vendor, Medidata, while the validation of the study-specific eCRFs will be conducted by AbbVie and will be maintained in the Trial Master File at AbbVie.

The investigator will document subject data in his/her own subject files. These subject files will serve as source data for the study. All eCRF data required by this protocol will be recorded by investigative site personnel in the EDC system. All data entered into the eCRF will be supported by source documentation.

The investigator or an authorized member of the investigator's staff will make any necessary corrections to the eCRF. All change information, including the date and person performing the corrections, will be available via the audit trail, which is part of the EDC system. For any correction, a reason for the alteration will be provided. The eCRFs will be reviewed periodically for completeness, legibility, and acceptability by AbbVie personnel (or their representatives). AbbVie (or their representatives) will also be allowed access to all source documents pertinent to the study in order to verify eCRF entries. The principal investigator will review the eCRFs for completeness and accuracy and provide his or her electronic signature and date to eCRFs as evidence thereof.

Medidata will provide access to the EDC system for the duration of the trial through a password-protected method of internet access. Such access will be removed from

investigator sites at the end of the site's participation in the study. Data from the EDC system will be archived on appropriate data media (CD-ROM, etc.) and provided to the investigator at that time as a durable record of the site's eCRF data. It will be possible for the investigator to make paper printouts from that media.

## **11.0 Data Quality Assurance**

Computer logic and manual checks will be created to identify items such as inconsistent study dates. Any necessary corrections will be made to the eCRF.

## **12.0 Use of Information**

All information concerning AbbVie DAA therapies and AbbVie operations, such as AbbVie patent applications, formulas, manufacturing processes, basic scientific data, or formulation information, supplied by AbbVie and not previously published, is considered confidential.

The information developed during the conduct of this clinical study is also considered confidential and will be used by AbbVie in connection with the development of AbbVie DAA therapy. This information may be disclosed as deemed necessary by AbbVie to other clinical investigators, other pharmaceutical companies, and governmental agencies. To allow for the use of the information derived from this clinical study and to ensure complete and thorough analysis, the investigator is obligated to provide AbbVie with complete test results and all data developed in this study and to provide direct access to source data and documents for study-related monitoring, audits, IRB review, and regulatory inspection.

This confidential information shall remain the sole property of AbbVie, shall not be disclosed to others without the written consent of AbbVie, and shall not be used except in the performance of this study.

The investigator will maintain a confidential subject identification code list of all subjects enrolled in the study, including each subject's name, subject number, address, phone

number, and emergency contact information. This list will be maintained at the study site with other study records under adequate security and restricted access, and will not be retrieved by AbbVie.

### **13.0 Completion of the Study**

The investigator will conduct the study in compliance with the protocol and complete the study within the timeframe specified in the contract between the investigator and AbbVie. Continuation of this study beyond this date must be mutually agreed upon in writing by both the investigator and AbbVie. The investigator will provide a final report to the IEC/IRB following conclusion of the study, and will forward a copy of this report to AbbVie or their representative. AbbVie will provide the Clinical Study Report to Regulatory Authority(ies), if required by local regulations.

The investigator must retain any records related to the study according to local requirements. If the investigator is not able to retain the records, he/she must notify AbbVie to arrange alternative archiving options.

AbbVie will select the signatory investigator from the investigators who participate in the study. Selection criteria for this investigator will include level of participation as well as significant knowledge of the clinical research, investigational drug and study protocol. The signatory investigator for the study will review and sign the final study report in accordance with regulatory authority guidance.

The end-of-study is defined as the date of the last subject's last visit.

## **Appendix A. Responsibilities of the Clinical Investigator**

Clinical research studies sponsored by AbbVie are subject to the Good Clinical Practices (GCP) and local regulations and guidelines governing the study at the site location. In signing the Investigator Agreement in Section 14.0 of this protocol, the investigator is agreeing to the following:

1. Conducting the study in accordance with the relevant, current protocol, making changes in a protocol only after notifying AbbVie, except when necessary to protect the safety, rights or welfare of subjects.
2. Personally conducting or supervising the described investigation(s).
3. Informing all subjects, or persons used as controls, that the drugs are being used for investigational purposes and complying with the requirements relating to informed consent and ethics committees (e.g., independent ethics committee [IEC] or institutional review board [IRB]) review and approval of the protocol and amendments.
4. Reporting adverse experiences that occur in the course of the investigation(s) to AbbVie and the site director.
5. Reading the information in the Investigator's Brochure/safety material provided, including the instructions for use and the potential risks and side effects of the investigational product(s).
6. Informing all associates, colleagues, and employees assisting in the conduct of the study about their obligations in meeting the above commitments.
7. Maintaining adequate and accurate records of the conduct of the study, making those records available for inspection by representatives of AbbVie and/or the appropriate regulatory agency, and retaining all study-related documents until notification from AbbVie.
8. Maintaining records demonstrating that an ethics committee reviewed and approved the initial clinical investigation and all amendments.

9. Reporting promptly, all changes in the research activity and all unanticipated problems involving risks to human subjects or others, to the appropriate individuals (e.g., coordinating investigator, institution director) and/or directly to the ethics committees and AbbVie.
10. Following the protocol and not make any changes in the research without ethics committee approval, except where necessary to eliminate apparent immediate hazards to human subjects.

ABT-493, ABT-530  
M13-576 Protocol Amendment 3  
EudraCT 2015-000452-24

---

**Appendix C. Study Activities A and B**

**Table A. SVR and Non-SVR Subjects Not Receiving Re-Treatment**

Activity	Day 1 a	Month 3 b,c	Month 6 b,c	Month 12 b,c	Month 18 b,c	Month 24 b,c	Month 30 b,c	Month 36 b,c
Informed Consent	X							
Medical History (related to liver disease/HCV infection) including past HCV drug treatments (during the prior study and before prior study)	X							
Assessment of Medical Events Related to Liver Disease/HCV Infection		X	X	X	X	X	X	X
Child-Pugh Score and Classification (cirrhotic subjects only) d	X		X	X	X	X	X	X
INR	X		X	X	X	X	X	X
Serum Albumin	X		X	X	X	X	X	X
IP-10 Sample	X	X	X			X	X (if final visit)	X
Clinical Chemistry Tests including Fibro Test and APRI (see Table 1 for details)	X	X	X	X f	X f	X	X (if final visit)	X
Platelets (for APRI)	X	X	X			X	X (if final visit)	X
HCV RNA Sample	X	X	X	X	X	X	X	X
HCV Resistance Sample	X	X	X	X	X	X	X	X
Archive Plasma Sample	X	X	X	X	X	X	X	X
Collection of Liver Diagnostic Results	X	X	X	X	X	X	X	X
HCC Screening Liver ultrasound for subjects with cirrhosis only (at Final visit only)	X g	X g	X g	X g	X g	X g	X g	X g

Activity	Day 1 a	Month 3 b,c	Month 6 b,c	Month 12 b,c	Month 18 b,c	Month 24 b,c	Month 30 b,c	Month 36 b,c
Assess for SAE related to Study Procedures or to Exposure to ABT-493 and/or ABT-530 in the prior study	X	X	X	X	X	X	X	X
Documentation of Medications for the Treatment of HCV or Treatment of an SAE Related to Study Procedures or to Exposure to ABT-493 and/or ABT-530 in the Prior Study	X	X	X	X	X	X	X	X
Collection of re-treatment regimen information and dosing dates (if applicable) e		X e	X e	X e	X e	X e	X e	X e

- a. The interval between the last dose of DAA therapy in the prior AbbVie clinical study and the Day 1 Visit of Study M13-576 must be no longer than 2 years.
- b. Once a subject has reached approximately 3 years post-DAA therapy, participation in Study M13-576 will be completed. The study visit which falls closest to 3 years since the subject's last dose of AbbVie DAA will be registered as their final visit.
- c. Visit window interval. Study visits should ideally take place within 3 weeks of the planned visit date. If the Month 3 visit is more than 6 weeks later than planned it should be registered instead as the Month 6 visit. If a Month 6, 12, 18, 24, 30 or 36 visit is more than 12 weeks later than planned it should be registered as the next visit in the schedule.
- d. Child-Pugh Score and Category should be assessed on all cirrhotic subjects (those cirrhotic upon enrollment and those who become cirrhotic during the study) after approval of Amendment 2 at the site.
- e. Subjects who are virologic failures and begin a re-treatment regimen during participation in the Study M13-576 will begin following the Study Activities Table B for re-treated subjects at the time re-treatment begins.
- f. Total bilirubin only will be collected at Month 12 and Month 18 for the Child-Pugh Score for cirrhotic subjects only.
- g. HCC Screening Liver ultrasound will be performed on subjects with cirrhosis at the visit considered the Final visit for the subject, unless the subject has a liver ultrasound, CT or MRI performed for HCC screening within 3 months prior to that visit, in which case the result of that US, CT or MRI will be used as the result for Final Study Visit assessment.

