## **5.0 Investigational Plan**

### **5.1 Overall Study Design and Plan: Description**

This Phase 2/3, multicenter study will be offered to subjects who received at least one dose of an ABT-493- and/or ABT-530-containing regimen at any dose level in an eligible prior AbbVie Phase 2 or 3 study for the treatment of chronic HCV and elect to enroll in this study. The subject must have completed the follow-up period of the prior eligible AbbVie study.

It is anticipated that approximately 400 subjects will participate in this study. An attempt will be made to enroll all virologic failures who will not receive immediate re-treatment with a regimen containing ABT-493/ABT-530.

At the Day 1 Visit, subjects will provide written (signed and dated) informed consent prior to any study specific procedures being performed. The investigator will evaluate whether the subject meets all of the eligibility criteria specified in Section 5.2.1 and Section 5.2.2 prior to enrollment in this rollover study.

Subjects will be followed for a total of approximately 3 years after their last dose of DAA in the previous HCV clinical study. The 3 years will be inclusive of any post-treatment period in the prior study, as well as any gaps between the end of the prior study and enrollment in this study. Subjects must complete the full post-treatment period of the prior study before enrolling into Study M13-576. Once a subject has reached 3 years post-DAA therapy, participation in this study will be completed, except for subjects enrolled with virologic failure who receive re-treatment with a HCV antiviral regimen other than investigational ABT-493/ABT-530. Subjects who are retreated with investigational ABT-493/ABT-530 are not allowed in this study. Subjects who are re-treated with HCV regimens other than investigational ABT-493/ABT-530 will have only one further assessment for treatment outcome 12 weeks after stopping that therapy or earlier if already known (in cases of treatment failure). (See [Appendix C](#), Table B, Study Activities for Virologic Failures Receiving Re-Treatment).

Subjects who have not been re-treated will return to the study site for their scheduled visits on an outpatient basis as described in Section 5.3.1 until approximately 3 years after their last dose of DAA in the previous clinical study (See Appendix C, Table A, Study Activities for SVR and Non-SVR Subjects Not Receiving Re-Treatment).

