### **5.2.1 Inclusion Criteria**

A subject will be eligible for study participation if he or she meets the following criteria:

1. The subject is male or female 18 years of age or older.
2. The subject has received at least one dose of an ABT-493- and/or ABT-530 containing regimen in a prior AbbVie HCV Phase 2 or 3 study (see Appendix D for list of eligible prior studies).
3. The interval between the last dose of the AbbVie DAA therapy from the previous clinical study and enrollment in Study M13-576 must be no longer than 2 years for subjects who have not been retreated. Subjects who have been treated with a commercially-available anti-HCV treatment may be enrolled greater than 2 years after the last dose of the AbbVie DAA therapy from the previous clinical study.
4. The subject must voluntarily sign and date the informed consent form approved by an Independent Review Board or Ethics Committee prior to the initiation of any study-specific procedures.
5. Subject completed the post-treatment period of an eligible prior study.

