### **8.1.3 Safety**

Serious adverse events will be coded using the Medical Dictionary for Regulatory Activities (MedDRA) and tabulated by system organ class (SOC) and preferred term (PT). A summary of medical events related to the progression of liver disease and shifts in laboratory measurements will be provided.

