6.0 Analysis Conventions

6.1 Definition of Baseline and Final Assessment

Definition of Baseline and Final Treatment Visit Value (Previous Study)

[figure not shown]
Baseline is defined as the last non-missing measurement before the first dose of study drug **in the previous study**. The final treatment visit value is defined as the last non-missing measurement collected after baseline and within 2 days of the last dose of study drug **in the previous study**.

Definition of Day 1 and Study Days (Study M13-576)

Day 1 refers to the Day 1 visit in Study M13-576. Study days in Study M13-576 are calculated for each time point relative to the Day 1 visit in this study. Study days are negative values when the time point of interest is prior to Day 1. Study days are positive values when the time point of interest is after Day 1. There is no Study Day 0. Study Days will be used to summarize hematology, clinical chemistry, and additional laboratory tests (IP-10, INR, and serum albumin) collected within this study.

Definition of Study Drug End Days (Days Relative to the Last Dose of Study Drug in the Previous Study)

Study drug end days are calculated relative to the last dose of study drug **in the previous study**. The last day of study drug is defined as Study Drug End Day 0. Days before it has negative study drug end days and days after it have positive study drug end days. Study

drug end days will be used to define the SVR windows from the previous study, and HCV RNA and resistance endpoints within this study.

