11.3 Analysis of Laboratory Data

Data collected from the central and local laboratories, including additional laboratory testing due to an SAE, will be used in all analyses.

Hematology variables include: platelet count

Chemistry variables include: total bilirubin, alpha-fetoprotein, gamma glutamyl transferase (GGT), alpha2-macroglobulin, AST, ALT, haptoglobin, and apolipoprotein A1.

Additional variables include: FibroTest, IP-10, INR, and serum albumin.

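### Non-retreated subjects who enter more than about 15 months after last dose have no FibroTest, APRI or IP-10 scheduled at their final visit, and the SAP's visit means from Month 24 on come only from earlier entrants

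*Protocol*

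**What the plan says.** Protocol section 5.1 sets the length of follow-up: "Subjects will be followed for a total of approximately 3 years after their last dose of DAA in the previous HCV clinical study". Any gap before enrolment counts towards the 3 years. Inclusion criterion 3 (section 5.2.1) says the gap "must be no longer than 2 years for subjects who have not been retreated". Note b to Appendix C Table A fixes the end of participation: "The study visit which falls closest to 3 years since the subject's last dose of AbbVie DAA will be registered as their final visit".

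Table A schedules IP-10, the FibroTest/APRI chemistry and platelets at Day 1 and Months 3, 6, 24 and 36, and at Month 30 only if that is the final visit. At Months 12 and 18 the IP-10 and platelet cells are empty. Note f covers the chemistry: "Total bilirubin only will be collected at Month 12 and Month 18 for the Child-Pugh Score for cirrhotic subjects only". The liver ultrasound row, by contrast, carries a final-visit note in every column.

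Summarising FibroTest, APRI and IP-10 is a secondary objective (Protocol 4.0, SAP 4.1). On the analysis side, SAP 6.1 states: "Study Days will be used to summarize hematology, clinical chemistry, and additional laboratory tests", with study days counted from Day 1 of this study. SAP 11.3.1 plans sample size, mean, SD, minimum, median and maximum at each visit. SAP 11.3 ends its variable list with "Additional variables include: FibroTest, IP-10, INR, and serum albumin". Protocol 8.1.3 commits to more, a summary in which "shifts in laboratory measurements will be provided".

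**The concern.** Table A recognises that an end-of-study marker value is wanted, because Month 30 gets the panel when it is the final visit. Months 12 and 18 can also be final visits, but they were not given the same condition. A subject who enters late therefore leaves the study with a last marker at Month 6.

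The effect carries into the tables. Late entrants contribute at Day 1, Month 3 and Month 6 and then disappear from the marker columns. Anyone reading the means from left to right would see time since treatment mixed with who enrolled early. With no within-subject change and no final-visit row, the planned output gives no means of separating the two.

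Two further mismatches between protocol and SAP affect the same tables. The promised laboratory shifts are not planned, and APRI is not in the SAP's variable list. SAP section 12, which lists departures from the protocol, mentions neither.

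**Working it through.** The documents give no figure for this point, so there is nothing to reproduce. The check applies the protocol's own visit rule.

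**Inputs.** Target: 36 months after last dose (Protocol 5.1; Table A note b). Entry gap g: up to 24 months if not retreated (Protocol 5.2.1). Visits m: Day 1 and Months 3, 6, 12, 18, 24, 30, 36 (Table A). Planned enrolment: about 400 (Protocol 5.1).

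**Final visit.** It is the m that minimises |g + m − 36|. The final visit switches between neighbouring visits m1 and m2 at g = 36 − (m1 + m2)/2:
- 36 and 30: 36 − 33 = 3 months
- 30 and 24: 36 − 27 = 9 months
- 24 and 18: 36 − 21 = 15 months
- 18 and 12: 36 − 15 = 21 months
- 12 and 6: 36 − 9 = 27 months, beyond the 24-month limit

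**Last panel.** Reading Table A at each final visit:

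| Entry gap (months) | Final visit | Last panel | Last panel, months after last dose | Months from last panel to final visit |
|---|---|---|---|---|
| under 3 | Month 36 | Month 36 | 36–39 | 0 |
| 3–9 | Month 30 | Month 30 | 33–39 | 0 |
| 9–15 | Month 24 | Month 24 | 33–39 | 0 |
| 15–21 | Month 18 | Month 6 | 21–27 | 12 |
| 21–24 | Month 12 | Month 6 | 27–30 | 6 |

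The 15-month boundary is approximate. Under note c, a Month 18 visit more than 12 weeks late is registered as Month 24 and would then carry the panel.

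**Who is in each marker column.** Day 1, Month 3 and Month 6: all Table A subjects. Month 24: g below about 15. Month 30: g about 3–9. Month 36: g below 3. The Month 30 and Month 36 groups do not overlap.

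**Share affected.** The distribution of g is not given. Assuming g uniform from a lower limit L to 24 months, the share with a Month 12 or 18 final visit is (24 − 15)/(24 − L):
- L = 3: 9/21 = 43% (171 if all 400 followed Table A)
- L = 6: 9/18 = 50% (200)
- L = 12: 9/12 = 75% (300)

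These are illustrations, not bounds. If everyone entered before 15 months the share would be 0%; if everyone entered at 15–24 months it would be 100%. The counts are also generous, because the 400 includes retreated subjects, who follow Table B.

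**Protocol against SAP.** Shifts: promised in Protocol 8.1.3 and the synopsis, absent from SAP 11.3 and 11.3.1. APRI: named in the objectives of both documents, absent from the SAP 11.3 list. SAP section 12 lists three changes, and neither of these is among them.

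**The case against.** The strongest reply is that nothing promised is lost. The objective is only to summarise results of these tests. Neither document commits to a 3-year marker value or a marker course, and late entrants' Day 1, Month 3 and Month 6 values are still summarised. That stands. A reader might infer that the secondary objective is defeated for late entrants, but the text does not support that; it is met less fully than the schedule could easily allow.

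A reader might also infer that the laboratory tables compare different subjects at every visit. They do not. The first three panel visits are scheduled for all Table A subjects, and the composition changes only from Month 24. The SAP plans no between-visit comparison, Protocol 5.6.1 calls the analyses purely descriptive, and the sample size is shown at each visit. The risk lies in how the columns will be read, and no size or direction of distortion can be derived.

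The point does not extend to every late entrant. Subjects retreated before enrolment may enter after 2 years, but they follow Table B, which schedules none of these tests, and they are outside the full analysis set.

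On APRI, the SAP's statement that each protocol-specified laboratory parameter will be summarised may be meant to include it. The missing entry is a lack of clarity, not proof that the analysis was dropped. No such reading rescues the shifts.

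Finally, HCV RNA, INR, albumin and liver events are collected at Months 12 and 18, as is Child-Pugh in cirrhotic subjects, and the final-visit ultrasound covers cirrhotic subjects. The gap is confined to FibroTest, APRI, IP-10 and the components not otherwise drawn. What remains is the schedule gap itself, for which the documents give no reason.

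**Conclusion.** The point holds for non-retreated subjects entering more than about 15 months after last dose. Their last scheduled FibroTest, APRI and IP-10 falls 6–12 months before the final visit. It follows directly from note b, note f and the 2-year entry limit, and the only approximation is the late-visit rule in note c.

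How many subjects this concerns cannot be determined from the documents. The 43%, 50% and 75% figures rest wholly on assumed uniform entry; none should be read as an estimate, and 75% is not an upper limit.

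The consequence for analysis is that marker means from Month 24 on describe progressively earlier entrants and should not be read as a time course alongside Day 1 to Month 6. The missing shifts are a separate, undisclosed departure from the protocol, and APRI needs to be named. All of this concerns a descriptive secondary summary and leaves the primary endpoints untouched. It should be corrected, but it does not threaten the study's main conclusions.

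**What to change.** **Protocol, Appendix C Table A.** At Months 12 and 18, enter the same if-final-visit condition that Month 30 carries, for IP-10, clinical chemistry including FibroTest/APRI, and platelets. Each Table A subject entering within 24 months would then have a scheduled final panel about 33–39 months after last dose.

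**SAP 11.3.** Add a final-visit row and paired change from Day 1 for FibroTest, APRI, IP-10 and platelets. List APRI explicitly. Add the shift summaries promised in Protocol 8.1.3, or record their removal in section 12. Windowing these markers by days since last dose, as the SAP does for HCV RNA, is optional.

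**Cost.** One added laboratory panel for the affected subjects, at a visit that already draws blood. It includes a platelet tube, since platelets are not scheduled at Months 12 and 18. The schedule change needs a minor protocol amendment with the IEC/IRB approval that Protocol 9.1 requires. The SAP changes need no new data and are worth making even if visits are complete. In that case the final-visit row would cover only subjects whose final visit was Month 24, 30 or 36, and a footnote should say so.
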